5.1 Treatment groups

The arms included in efficacy tables are based on the treatment sequence (picturing also the up-titration) for the periods up to the final lock at week 260. Two separate columns will display the assigned and actual treatment resulting in the following treatment sequences:

Efficacy:

- AIN457 10 mg/kg - 75 mg
- AIN457 10 mg/kg - 75 mg - 150 mg
- AIN457 10 mg/kg - 75 mg - 300 mg
- AIN457 10 mg/kg - 150 mg
- Placebo - AIN457 75 mg
- Placebo - AIN457 75 mg - 150 mg
- Placebo - AIN457 75 mg - 300 mg
- Placebo - AIN457 150 mg

After week 52 the combination of assigned treatment will also be shown.

- AIN457 75 mg & Placebo - AIN457 75 mg
- AIN457 150 mg & Placebo - AIN457 150 mg

The treatment sequence following up-titration for the combined groups will be:

- AIN457 75 mg & Placebo - AIN457 75 mg - 150 mg
- AIN457 75 mg & Placebo - AIN457 75 mg - 300 mg
- AIN457 150 mg & Placebo - AIN457 150 mg – 300 mg

Cases might up-titrate twice; for these cases the treatment prior to each up-titration will be displayed (that is not the assigned treatment for the 2nd observed up-titration). Therefore, at the graphical representation of up-titration the actual treatment dose prior to the switch will be displayed.

Regarding safety, the arms included in the entire treatment period are as follows.

- Any AIN457 75 mg
- Any AIN457 150 mg
- Any AIN457 300 mg
- Any AIN457 (if appropriate)

Placebo group will be included at the in-text tables and listings of the CSR.

In the safety listings the groups will be the following:

- AIN457 10 mg/kg - 75 mg
- AIN457 10 mg/kg - 150 mg
- Placebo AIN457 75 mg
- Placebo AIN457 150 mg
- Placebo not re-randomized.

6 Subgroup definitions

The primary endpoint and secondary endpoints will be evaluated for TNF-alpha inhibitor status and by concomitant MTX use (ACR20/50, [REDACTED]).

7 Assessment windows, baseline and post baseline definitions, missing data handling

Baseline and post-baseline definitions

In general, a *baseline* value refers to the core study and is the last measurement made prior to administration of the first dose of study treatment in core. Baseline information will be presented appropriately in the “by visit” summaries in both safety and efficacy tables.

A post-baseline value refers to a measurement taken after the first dose of study treatment in core study.

Analysis visit windows

For visits that occur on or before week 104, *analysis visit windows* will be used for the data that is summarized by visit; they are based on the study evaluation schedule and comprise a set of days around the nominal visit day. For any assessment, there are protocol defined scheduled visits around which analysis visit windows were created to cover the complete range of days within the study. The analysis visit windows and rules for dealing with multiple measurements within the windows are described in the [Appendix \(17.1 Visit Windows\)](#).

For visits that occur after week 104, the recorded nominal visit data will be considered.

8 Subject disposition, background and demographic characteristics

8.1 Subject disposition

The number of subjects enrolled in the extension will be presented. The number and percentage of subjects in the FAS who completed the period up to week 260 and/or the follow up visit and who discontinued the study prematurely (including the reason for discontinuation) will be presented for each treatment group (including the up-titrated groups).

For each protocol deviation (PD), the number and percentage of subjects for whom the PD applies will be tabulated.

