From the standpoint of the overall risk-benefit assessment, the current trial with secukinumab is justified.

4 Population

Eligible subjects are those who complete the full study treatment period of the core study (CAIN457F2306) and comply with the eligibility criteria of this extension study. These criteria include signed Informed Consent and/or Amended Informed Consent specific to CAIN457F2306E1 and the subject being deemed by the investigator to benefit from continued secukinumab therapy.

In total, 460 patients were enrolled in study CAIN457F2306E1.

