5.5.12 Early study termination

The study can be terminated at any time for any reason by Novartis. Should this be necessary, the subject should be seen as soon as possible and treated as a prematurely withdrawn subject. The investigator may be informed of additional procedures to be followed in order to ensure that adequate consideration is given to the protection of the subject's interests. The investigator will be responsible for informing IRBs and/or ECs of the early termination of the trial.

6 Visit schedule and assessments

Table 6-1, Table 6-2 and Table 6-3 list all of the assessments and indicate with an "X" when the visits are performed.

Subjects should be seen for all visits on the designated day or as close to it as possible. Subjects should not receive study medication within less than 2 weeks after the previous administration.

During the treatment periods, subjects may be seen at an unscheduled visit, e.g. if they experience deterioration of their condition, or AEs that in the opinion of the investigator need intervention or repeated laboratory testing. During these unscheduled visits, study treatment will not be administered. Subjects who discontinue study treatment will continue to be followed for safety assessments. They are not considered withdrawn from the study.

Subjects who discontinue study treatment before completing the study, and those who prematurely withdraw from the study for any reason should be scheduled for a study visit 4 weeks after their last study treatment administration, at which time all the assessments listed for EoT for the given treatment period (Week 156 or 208 or 260) will be performed (see [Section 5.5.9](#)). Subjects will then return to the study site 12 weeks after the last study treatment administration for further assessments as indicated under the follow-up visits (F268).

If they refuse to return for these assessments or are unable to do so, every effort should be made to contact them or a knowledgeable informant by telephone or by sending appropriate correspondence (i.e. certified letter) immediately. At this contact, the safety (e.g., potential occurrence of AE or SAE) and the primary reason for a subject's premature withdrawal should be determined.

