At a minimum, subjects will be contacted for safety evaluations during the 12 weeks following the last study visit or following the last administration of study treatment (whichever is later), including a final contact at the 12-week point. Documentation of attempts to contact the subject should be recorded in the source.

Order of assessments:

- Subject to complete PROs prior to any investigator assessments.
- Investigator to complete investigator assessments (Physician's global assessment of disease activity)
- All remaining study visit procedures (e.g., laboratory sample collection, vital signs measurements etc.) must be completed prior to study treatment dosing.
- Study treatment administration (administration by site staff or self-administration as per assessment schedule).

Table 6-1 Assessment schedule (Week 104E1 to Week 156)

Epoch	Treatment Period 3													
	104E1	108	112E1	116	120	124	128	132	136	140	144	148	152	156 and TD and/or PSW
Informed consent	X													
Inclusion/exclusion criteria	X													
Physical examination	*			S			S			S				S
Weight	*						X							X
Vital signs	*			X			X			X				X
ECG	*						X							X
Administration of s.c. study treatment via PFS at study site	X	X	X	X	X	X	X			X				X
Administration of s.c. study treatment via PFS at home ¹								X	X		X	X	X	
Hematology, blood chemistry, urinalysis	*			X			X			X				X
Urine pregnancy test ²	*			X			X			X				X
Concomitant medication/non-drug therapy	Update as necessary throughout the study													
AE/SAE (including injection site reaction, occurrence of infection)	Update as necessary throughout the study													
X-Ray (hands/wrists + feet)	*													X ⁵
ANA	*													X
Anti-dsDNA	*													X
PK assessments (at pre-dose)	*													X
High sensitivity C-Reactive protein (hsCRP)	*			X			X			X				X
Erythrocyte Sedimentation Rate (ESR) ²	*			X			X			X				X
Tender and swollen joint counts (TJC78, SJC76)	*			X			X			X				X
Patient's assessment of PsA pain (VAS)	*			X			X			X				X
Patient's global assessment of disease activity (VAS)	*			X			X			X				X
Physician's global assessment of disease activity (VAS)	*			X			X			X				X
Health Assessment Questionnaire (HAQ-DI)	*			X			X			X				X

Epoch	Treatment Period 3													
Week (relative to baseline of core study CAIN457F2306)	104E 1	108	112 E1	116	120	124	128	132	136	140	144	148	152	156 and TD and/or PSW
[REDACTED]														
[REDACTED]														
Lipids ⁴	*						X							X

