Cardiovascular panel	*													X
Treatment period 3 completion form														X

TD = Investigational treatment discontinuation; **PSW** = Premature subject withdrawal. Subjects who prematurely discontinue treatment or are withdrawn prematurely during treatment period 3 should return for assessments associated with Week 156 (4 weeks after last study treatment) and the follow-up visit (Week F268) 12 weeks after last study treatment.

X = assessment to be recorded in clinical data base

S = assessment to be recorded on source documents

* These assessments shall be conducted as part of the core study CAIN457F2306 and will not be repeated in this extension study

¹ Subjects who are unable to self-administer the PFS injection at home will visit the site and site staff will administer PFS injection for them

² Kits will be provided by central lab and tests are to be performed locally

[REDACTED]

⁴ Fasting (more than 12 hours) samples to be obtained

⁵ Subjects who discontinue will have their X-rays taken only if more than 6 months have elapsed since their last X-rays

[REDACTED]

Table 6-2 Assessment schedule (Week 160 to Week 208)

Epoch	Treatment Period 4												
	160	164	168	172	176	180	184	188	192	196	200	204	208 and TD and/or PSW
Physical examination			S			S			S				S
Weight						X							X
Vital signs			X			X			X				X
ECG						X							X
Administration of s.c. study treatment via PFS at study site			X			X			X				X
Administration of s.c. study treatment via PFS at home ¹	X	X		X	X		X	X		X	X	X	
Hematology, blood chemistry, urinalysis			X			X			X				X
Urine pregnancy test ²			X			X			X				X
Concomitant medication/non-drug therapy	Update as necessary throughout the study												
AE/SAE (including injection site reaction, occurrence of infection)	Update as necessary throughout the study												
X-Ray (hands/wrists + feet)													X ⁵
ANA													X
Anti-dsDNA													X
PK assessments (at pre-dose)													X
High sensitivity C-Reactive protein (hsCRP)						X							X
Erythrocyte Sedimentation Rate (ESR) ²						X							X
Tender and swollen joint counts (TJC78, SJC76)						X							X
Patient's assessment of PsA pain (VAS)						X							X
Patient's global assessment of disease activity (VAS)						X							X
Physician's global assessment of disease activity (VAS)						X							X
Health Assessment Questionnaire (HAQ-DI)						X							X

[Redacted footer text]

Epoch	Treatment Period 4												

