Extension Full analysis set (extension FAS): The extension FAS will be comprised of all subjects enrolled in the extension study and have at least one post baseline assessment of efficacy during the extension period. Subjects will be analyzed according to the treatment assigned to.

(In this document extension FAS is referred as to FAS).

Of note, FAS will comprise only the subjects from extension whereas safety set will include from core or extension, safety set will be larger than FAS.

Up-titration Subset: The up-titration subset will be comprised of subjects from the extension FAS set who received at least one dose of the up-titration dose.

Psoriasis subset: The psoriasis subset will include all FAS subject who have $\geq 3\%$ of the body surface area (BSA) affected by psoriatic skin involvement at baseline.

Nail subset: The nail subset will include all FAS subject who have psoriasis currently in nails at baseline.

Safety set: The safety set includes all subjects who took at least one dose of study treatment during the treatment period in core or extension study. Subjects will be evaluated according to treatment received.

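### SAP 8.1 bases completion and discontinuation percentages on the extension FAS, which can leave out only non-completers, so the discontinuation rate is understated whenever anyone is excluded

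*SAP*

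**What the plan says.** SAP 8.1 starts from everyone who entered, but only as a count: "The number of subjects enrolled in the extension will be presented". It then changes base for the rest of the disposition table: "The number and percentage of subjects in the FAS who completed the period up to week 260". Premature discontinuation and its reasons are on the same base, by treatment group including the up-titrated groups.

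SAP Section 5 defines the extension FAS as subjects who enrolled and "have at least one post baseline assessment of efficacy during the extension period". It adds: "In this document extension FAS is referred as to FAS". The FAS in 8.1 is therefore this restricted set. The safety set is not an alternative base, because it includes anyone dosed in either the core or the extension study.

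Protocol Section 4 gives the number of entrants: "In total, 460 patients were enrolled in study CAIN457F2306E1". Neither document plans completion or discontinuation percentages on that number.

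The efficacy assessments at Week 104E1 carry an asterisk in Protocol Table 6-1. The footnote reads: "These assessments shall be conducted as part of the core study CAIN457F2306 and will not be repeated in this extension study". In the visible rows, such as "Tender and swollen joint counts (TJC78, SJC76)", the first mark after the asterisk is at Week 116.

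**The concern.** A disposition table shows how many people who entered did not finish, and why. If its base requires an assessment that some early leavers never had, those leavers disappear from the table that should count them.

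This matters more here than in a study with a missing-data model. SAP 12.3 reports efficacy on observed data only and drops both multiple imputation and MMRM. Protocol 3.1 and 5.5.9 tell investigators to discontinue subjects who are not benefiting, so leaving may be related to outcome. Disposition is then an important guide to how selected the remaining responders are, and it should not be calculated after some of the earliest leavers have been set aside.

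**Working it through.** **The plan's own figure.** Neither document states a FAS size or an expected discontinuation rate. The only calculated number is the expected entry of 460 to 520 (Protocol 9.7, SAP Section 16). It reproduces: the bases implied by 320/0.80 and 360/0.90 are 400, and by 140/0.70 and 160/0.80 are 200. Then 0.80 × 400 + 0.70 × 200 = 460, and 0.90 × 400 + 0.80 × 200 = 520. Actual entry was 460.

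**Who can be excluded.** An entrant is outside the FAS only if all of the following hold:

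1. The subject leaves before the first scheduled extension efficacy visit. In the visible rows of Table 6-1 this is Week 116, 12 weeks after entry. Some rows are redacted, so an earlier assessment cannot be ruled out.
2. The subject provides no efficacy data at the end-of-treatment visit 4 weeks after the last dose, "at which time all the assessments listed for EoT for the given treatment period (Week 156 or 208 or 260) will be performed" (Protocol Section 6). For treatment period 3 these include joint counts, VAS scores, HAQ-DI, hsCRP and ESR.
3. The subject provides no efficacy data at the follow-up visit 12 weeks after the last dose. Table 6-3 marks hsCRP and ESR there, and Protocol 6.4 lists both as efficacy measures.

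Protocol Section 6 foresees subjects who will not or cannot return. It provides telephone or written contact for them, which yields no efficacy data. The excluded group can therefore exist, but the route into it is narrow.

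**Why every excluded subject is a non-completer.** Protocol 5.5.11 requires a completer to have been treated to the planned end and to have had the scheduled assessments through Visit F268. A subject with no extension efficacy assessment cannot meet that.

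**Formula.** Let N be the number enrolled, d all premature discontinuations, and k the entrants outside the FAS.

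- Rate on all enrolled: d/N
- Rate on the FAS: (d − k)/(N − k)
- Difference: d/N − (d − k)/(N − k) = k(N − d)/[N(N − k)]

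The difference is above zero for any k > 0 with d < N, and zero at k = 0.

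**Numbers.** N = 460. Neither k nor the final d is in the documents, so both are assumed over a range. The value d = 28 is 460 − 432, from the Amendment 1 rationale, and serves only as an illustration. The other values of d are 15%, 20% and 30% of 460.

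| d | All enrolled | FAS, k = 1 | FAS, k = 5 | FAS, k = 10 | FAS, k = 28 |
|---|---|---|---|---|---|
| 28 | 6.09% | 5.88% | 5.05% | 4.00% | 0.00% |
| 69 | 15.00% | 14.81% | 14.07% | 13.11% | 9.49% |
| 92 | 20.00% | 19.83% | 19.12% | 18.22% | 14.81% |
| 138 | 30.00% | 29.85% | 29.23% | 28.44% | 25.46% |

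For d = 92: k = 5 gives 87/455 = 19.12%, and k = 10 gives 82/450 = 18.22%. At k = 1 the gap runs from 0.15 points (d = 138) to 0.20 points (d = 28). For k = 5 it is 0.8 to 1.0 points, and for k = 10 it is 1.6 to 2.1 points. The column k = 28 is an outer case, in which as many subjects as were off treatment in September 2015 had no extension efficacy data at all.

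**The case against.** The strongest reply is that the effect may be close to nothing. Two return visits can each qualify an early leaver, the documents give no count of exclusions, and the gap is zero if there are none. That stands, and it limits the size of the point.

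A second reply is that overall completion can be recovered. The enrolled count is reported and every excluded subject is a non-completer, so FAS completers divided by 460 gives the right overall figure. The arithmetic is correct. It does not repair the planned percentages, which remain on the restricted base, and it does not supply the excluded subjects' discontinuations by group or their reasons. Adverse events causing discontinuation, and deaths, are summarised in the safety set (SAP 14.1). That covers those causes but not lack of efficacy, withdrawal of consent or loss to follow-up.

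A third reply is that excluded subjects have no extension efficacy data, so a FAS disposition table describes the population of the efficacy tables. This is true, and a reason to keep a FAS display if one is wanted. It does not show how many entrants were lost before that population was formed.

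A reader might also infer something stronger: that 28 of 460 had left the study by September 2015, and that 5 or 10 exclusions would make the reported rate one-sixth to one-third too low (23/455 = 5.1% or 18/450 = 4.0%, against 6.1%). The documents do not support that reading. The Amendment 1 rationale says how many were still under treatment, and Protocol Section 6 says that stopping study treatment is not withdrawal from the study. The date is also interim, whereas SAP 8.1 runs to Week 260. The relative gap shrinks as discontinuations accumulate: with an assumed 92, it is about 4% for 5 exclusions (19.1 against 20.0) and 9% for 10 (18.2 against 20.0).

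**Conclusion.** The point holds as a matter of direction, with a modest and unknown size. On the stated rules, the FAS can lose only non-completers, so the planned discontinuation rate is too low, and the completion rate too high, whenever anyone is excluded. The gap is about 0.15 to 0.2 percentage points per excluded subject. At an assumed 20% final discontinuation it is 0.9 points for 5 exclusions and 1.8 points for 10. The reasons for leaving of those subjects are not tabulated under this plan.

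This rests on two readings. The first is that Week 104E1 efficacy data belong to the core study and do not qualify a subject for the extension FAS, as the Table 6-1 footnote indicates; if they did qualify, k would be near zero. The second is that completion follows Protocol 5.5.11. The number excluded is probably small. The study is descriptive, so no hypothesis test is affected, and the efficacy tables do not change.

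**What to change.** In SAP 8.1, use all subjects enrolled in the extension (460) as the denominator for completion, premature discontinuation and reasons for discontinuation, overall and by originally assigned treatment group. Keep the up-titrated groups as an additional display. Add a line giving the number of enrolled subjects excluded from the FAS, with the reason for exclusion and their reasons for discontinuing.

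Protocol 5.5.9 already requires the primary reason for withdrawal to be recorded, so no new data are needed. The cost is SAP wording and a stated completion rate that may be slightly lower.

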According to protocol exclusion criterion #4 women of child-bearing potential, currently defined as all women physiologically capable of becoming pregnant and unwilling to use effective contraception during the study and for 16 weeks after stopping treatment, should not be considered eligible for the study. However, there are approved secukinumab labels for the psoriasis indication that indicate a specific time window for the use of effective contraception after stopping treatment. There is currently no evidence to indicate that a specific duration of post-treatment contraception is required for patient safety. However, to align with these specifications in local prescribing information, protocol exclusion criterion #4 is changed to

“Women of child-bearing potential (WoCBP), defined as all women physiologically capable of becoming pregnant, unless they are using effective methods of contraception during the entire study or longer if required by locally approved prescribing information (e.g. 20 weeks in EU).”

3. Data monitoring committee review no longer required

Based on the safety results of studies CAIN457F2306 and CAIN457F2312, the DMC review will no longer be required.

None of the changes described in this amended protocol are due to evidence-based safety concerns.

At the time of this amendment, enrolment into the extension study was complete with 460 patients enrolled and 432 patients still under treatment as of September 6, 2015.

Changes to the protocol

Changes to specific sections of the protocol are shown in the track changes version of the protocol using strike through red font for deletions and red underlined for insertions.

The wording of various sub-sections to “Study objectives” ([Section 2](#)) “Investigational Plan” ([Section 3](#)), “Population” ([Section 4](#)), “Treatment” ([Section 5](#)), “Data analysis” ([Section 9](#)), “Data Monitoring Committee” ([Section 8.4](#)) and “Appendix 4” ([Section 13.4](#)) have been amended to reflect the rationale given above.

Additionally, this protocol amendment includes the correction of typographical and formatting errors and editorial changes for increased clarity of the text. Consequently, changes were implemented throughout the protocol.

A copy of this amended protocol will be sent to the Institutional Review Board (IRBs)/Independent Ethics Committee (IECs) and Health Authorities.

The changes described in this amended protocol require IRB/IEC approval prior to implementation.

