- Group 2: secukinumab 150 mg (1mL) once every four weeks till (and including) Week 256. After approval and implementation of Amendment 1, patients may be escalated to 300 mg as judged appropriate by the investigator.

Study treatment dose adjustments are not permitted until Week 156.

Starting from Week 156 (i.e. during the open label study period), after approval and implementation of Amendment 1, the secukinumab dose should be escalated from 75 mg to 150 mg for patients whose signs and symptoms are not fully controlled with the current dose of 75 mg, and may improve with higher dose as judged by the investigator.

Further, the dose should also be escalated to 300 mg for patients currently on 75 mg or 150 mg, and whose signs and symptoms are not fully controlled and may improve further with an increase in dose as judged by the investigator.

Dose escalation from secukinumab 75 mg to 300 mg can be done either in one step or in two steps (first 150 mg, then 300 mg based on investigator's judgement).

For patients escalated to 150 mg or 300 mg, no dose reduction can be performed at a later stage.

Subjects will continue to be on background methotrexate (MTX) (if they were already taking MTX at the start of core study CAIN457F2306) throughout the study. The dose of MTX may be adjusted as deemed appropriate by the investigator.

In addition subjects will be allowed to start or adjust the dose of corticosteroids and non-steroidal anti-inflammatory drugs (NSAIDs) as deemed appropriate by the investigator.

[figure not shown]
Before enrolment in this extension study, all subjects electing to continue will sign an Informed Consent form. After approval and implementation of Amendment 1, all subjects electing to continue will sign a new version of the Informed Consent form. Detailed instructions for self-administration of the s.c injection using the PFS formulation will be provided to each subject. Each injection will be administered into an appropriate injection site of the body. For the first 6 months of the extension study (up to Week 128), all injections will be performed at site. Starting from Week 132 subjects will have the choice of self-administration at home or continuing with administration at site, based on personal preference and the investigator's clinical judgment. Site staff or caregiver (once trained) will administer the injection to subjects who are not able or feel insecure to self-administer the PFS injection.

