5.5.5 Permitted dose adjustments and interruptions of study treatment

Study treatment dose adjustments are not permitted until Week 156.

After approval and implementation of Amendment 1, patients previously treated with secukinumab 75 mg may receive either 75 mg, 150 mg or 300 mg, and patients previously treated with secukinumab 150 mg may receive 150 mg or 300 mg, as deemed appropriate by the investigators. The decision may be taken at any on-site visit. When dose escalation has been performed for one patient, no dose reduction can be performed at a later stage.

Study treatment interruption is also not permitted with the following exceptions:

- Study treatment interruption is permitted only if, in the opinion of the investigator, a subject is deemed to be placed at a significant safety risk unless dosing is temporarily interrupted. In such cases study treatment should be interrupted only during the time that this risk is present and ongoing. Study treatment can be restarted at the next scheduled visit after resolution of the safety risk.
- The effect of secukinumab on live vaccines is unknown; therefore live vaccines should not be administered during participation in the study. In case a live vaccine has been

administered due to a medical urgency, study treatment should be interrupted for 12 weeks.

The reason for any study treatment interruption must be recorded on the corresponding eCRF page.

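### Retention percentages for the up-titrated groups in SAP 8.1 are biased upward against the non-escalated groups, because a subject must stay on treatment until escalation to be counted there

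*SAP*

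**What the plan says.** SAP 8.1 counts, in the extension FAS, "The number and percentage of subjects in the FAS who completed the period up to week 260 and/or the follow up visit", and likewise those "who discontinued the study prematurely (including the reason for discontinuation) will be presented for each treatment group (including the up-titrated groups"). The percentages cover the whole extension. The section sets no landmark, does not count from the escalation date, and gives no caveat on the up-titrated columns.

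Four other provisions determine who can appear in those columns:

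- SAP section 5 defines the up-titration subset as extension FAS subjects "who received at least one dose of the up-titration dose".
- Protocol 3.1: "Study treatment dose adjustments are not permitted until Week 156". That is 52 weeks after entry at Week 104, and escalation also needs Amendment 1 to be approved and implemented.
- Protocol 5.5.5, on escalation: "The decision may be taken at any on-site visit".
- The same section makes escalation irreversible: "When dose escalation has been performed for one patient, no dose reduction can be performed at a later stage".

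The Amendment 1 rationale reports "460 patients enrolled and 432 patients still under treatment as of September 6, 2015".

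**The concern.** Column membership depends on an event after entry that only subjects still on treatment can experience. Nobody in an up-titrated column can have left before escalating. Every FAS subject who left earlier must be in a non-escalated column, including anyone who left for lack of benefit before escalation was on offer. This is immortal-time bias. It is separate from the selection of poorly controlled subjects for escalation, and would arise even if escalation were random and dose had no effect on staying in the study.

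SAP 2 and 12.3 drop multiple imputation and MMRM and rely on observed data, so a reader will look to disposition to see who is missing from the ACR percentages and why. With escalated and non-escalated columns side by side, part of any apparent retention advantage at the escalated doses would come from the way the columns are formed. The reasons for leaving are affected too, because all pre-escalation exits load onto the non-escalated columns.

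**Working it through.** The documents give no expected retention or escalation rate, so there is no planned figure to reproduce. The check asks what the SAP 8.1 table would show if dose had no effect.

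**From the documents.** Enrolled 460; still under treatment at the Amendment 1 count 432; difference 460 − 432 = 28 (28/460 = 6.1%). None of the 28 could have received an escalated dose.

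**Assumed.** Discontinuation rate λ = 0.05 per year in everyone; a fraction p = 0.40 of the 432 would escalate, at a uniform time in year 1 if still on treatment; follow-up F = 2 years; the 28 counted as discontinuations.

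**Escalated columns**
- Mean probability of reaching escalation: (1 − e^−0.05)/0.05 = 0.9754.
- Number escalated: 432 × 0.40 × 0.9754 = 168.6.
- Completers among them: 432 × 0.40 × e^−0.10 = 156.4.
- Discontinued: 12.2, and 12.2/168.6 = **7.2%**.

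**Non-escalated columns**
- Number: 432 − 168.6 + 28 = 291.4.
- Left before an intended escalation: 172.8 − 168.6 = 4.2.
- Never due to escalate and left: 259.2 × (1 − e^−0.10) = 24.7.
- Discontinued: 4.2 + 24.7 + 28 = 56.9, and 56.9/291.4 = **19.5%**.

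The gap is 12.3 points with no true difference. Over λ = 0.03 to 0.08, p = 0.2 to 0.6 and F = 1.5 to 2 years, the same formulas give 3.0–11.3% against 11.9–30.2%, a gap of 8.8 to 19.6 points.

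**How much rests on the 28.** Leaving them out of the central case gives (4.2 + 24.7)/(432 − 168.6) = 28.9/263.4 = 11.0%, against 7.2%. The gap is then 3.7 points, and 1.8 to 8.5 over the same range. This version starts the clock at Amendment 1 and so ignores the first part of the extension. A second version avoids the 28 but covers all of Weeks 104–260. It assumes a constant hazard with 10% dropout over the three years and half of subjects due to escalate at a uniform time in Weeks 156–208. The mean probability of reaching escalation is 0.9487. Retention is 0.90/0.9487 = 94.9% in escalated and 0.45/(1 − 0.5 × 0.9487) = 85.6% in non-escalated columns, a gap of 9.3 points.

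**When the ordering reverses.** In the central case let the hazard after escalation be h times the common one. The proportion discontinued after escalation is 1 − e^(−hλF) × [(e^((h−1)λ) − 1)/((h−1)λ)]/0.9754. This gives 13.9% at h = 2, 19.5% at h = 2.9 and 20.1% at h = 3. With the 28 counted, a doubled exit rate after escalation would still look like better retention, and the gap closes at about h = 2.9. Without the 28 it closes at about h = 1.55 (11.0%).

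**What person-time would show.** In the central case, discontinuations divided by subject-years are 12.2/243.9 after escalation and 28.9/578.3 in time not yet escalated from Amendment 1. Both are 5.0 per 100 subject-years, so the artefact is gone.

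**The case against.** - **The ordering is not fixed.** A reader might infer that the table must show the escalated doses as better retained whatever the drug does. The documents do not support that. Protocol 3.1 directs escalation to subjects whose disease is not fully controlled and tells investigators to discontinue those not benefiting, so escalated subjects may leave faster. Only the direction of the bias is guaranteed. This stands.
- **Tolerability by dose is handled elsewhere.** Protocol 6.5.7 assesses tolerability by adverse events, laboratory values and injection-site reactions, not retention. SAP 14 splits dose-escalated subjects' exposure by start and stop date, and 14.1 plans exposure-adjusted rates for adverse events leading to discontinuation. This stands. It leaves overall retention and exits for lack of efficacy or other reasons uncovered.
- **The table is descriptive.** No hypothesis is tested, no dose comparison is planned, and retention is not an objective. This stands; the harm is misreading, not an error rate.
- **The 28 are not the table's count.** They are patients no longer under treatment. SAP 8.1 counts study discontinuations in the FAS, protocol section 6 says stopping treatment is not withdrawal, and FAS entry needs an extension efficacy assessment. A reader might take 28 as documented discontinuations in this table; it is only an input to the illustration.
- **Assigned-dose columns may be there.** SAP 5.1 plans combined assigned-dose groups, but for efficacy tables. SAP 8.1 neither excludes nor commits to them, and adding them would not remove the bias in the up-titrated columns.
- **The up-titrated columns have a use.** They match the efficacy columns and show why those denominators shrink. This is a fair reason to keep them, with a caveat.

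**Conclusion.** The concern holds as an upward bias in escalated-column retention relative to the non-escalated columns. It follows from the definitions in the documents and needs no assumption about the drug. Its size does rest on assumptions: with random escalation and equal hazards, about 7% against 19.5% discontinued in the central case, or 7.2% against 11.0% if the 28 are left out. These figures show what the layout produces under no effect; they do not forecast the table. In a descriptive table whose safety side is already partly covered, this is a worthwhile and inexpensive improvement. It does not threaten the primary ACR analysis.

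**What to change.** In SAP 8.1:

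1. State that completion and discontinuation, with reasons, are given by assigned dose (75 mg, 150 mg, total) as the primary display.
2. Keep the up-titrated columns only with a footnote that they are conditional on remaining on treatment until escalation.
3. Add a table counted from the first escalated dose: number escalated, number discontinued afterwards by reason, subject-years, and rate per 100 subject-years. Set beside it the rate in not-yet-escalated time from when escalation became available, with escalators contributing there until they escalate.
4. State that the two rates are descriptive, because escalation was chosen for inadequate control and the groups are not comparable.

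The cost is SAP wording and one extra table from dates the study already records. Trial conduct does not change.
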